1 AMENDMENT HISTORY

Amendment No.	Protocol Version No.	Date issued	Author(s) of changes	Details of Changes made
Protocol amendment 1 (Amendment ref. SA02)	1.0	23-Oct-13	[name] [name]	Update to consent section; replacement of initial verbal consent with use of a single page combined patient information sheet and consent form at the point of hospital admission.
Protocol Amendment 2 (Amendment ref: SA08)	2.0	11-Feb-14	[name] [name]	Addition of Appendix B (mechanistic sub-study)Correction made to section 6.3.3 that trial treatment will be discontinued if participant is later found to meet exclusion criteria.Added that an appropriately trained research nurse may take written consent.Added that treatment pack will also contain a spoon for drug administration and a wristband for trial participantsMinor spelling corrections/administrative changes.

2 SYNOPSIS

Study Title	Early low dose steroids for adults admitted to hospital with influenza-like illness during a pandemic: a randomised placebo-controlled trial			
Internal ref. no.	11RM013			
Clinical Phase	Phase III			
Trial Design	Pragmatic multi-centre double-blind randomised trial			
Trial Participants	Adults (≥ 16 years old) hospitalised with an influenza-like illness during a pandemic.			
	2200 patients.			
Planned Sample Size	The planned sample size is based on the range of possible scenarios that might be encountered during a pandemic. With 2200 patients, the study will have 90% power to detect a 15% relative reduction in the primary outcome (admission to intensive care or death).			
Follow-up duration	Patients will be asked to complete a follow-up questionnaire 30 days after hospital discharge. Completion of the questionnaire is not required for patients hospitalised ≥60 days. Patient outcome information will be collected from hospital-based system records for these patients.			
	The trial is unique as it will be set up pre-pandemic. Once set-up is complete and all the required approvals have been obtained, the trial will be placed into 'hibernation'.			
	After the initial set-up, there will be 3 distinct phases to the trial.			
	1) Hibernation phase During hibernation, regular review (at least annually) of trial procedures and sites will ensure that the trial is maintained in a state in which it can be readily activated to start recruitment in the event of a pandemic.			
Planned Trial Period	2) Pre-activation phase When the National Institute for Health Research (NIHR) decide to activate the trial, a pre-activation phase of four to six weeks will begin immediately. This will include final review of trial procedures, trial drug production and distribution, production and distribution of trial materials and a check of site readiness prior to beginning recruitment.			
	3) Activation phase During activation, patients will be recruited into the trial. Recruitment Is planned to be completed within the first pandemic wave, typically of six weeks duration. This phase also includes data collection and follow-up.			
Primary Objective	To determine whether during a pandemic, for adults (\geq 16 years) hospitalised with an influenza-like illness, a 5-day course of dexamethasone started within 24 hours of admission to hospital, in addition to standard care, is associated with a lower risk of death or admission to intensive care compared to placebo.			
Secondary Objectives	To determine whether dexamethasone given in addition to standard care is associated with a reduction in the length of hospital stay, the frequency of hospital readmission and/or the frequency of GP consultations after discharge compared to placebo. If dexamethasone is effective, the study will also evaluate its cost-effectiveness.			

Primary Endpoint	Admission to intensive care unit or death, within 30 days of hospital admission				
Secondary Endpoints	 Length of stay in intensive care unit Readmission within 30 days of hospital discharge GP consultations within 30 days of hospital discharge Length of stay in hospital Death within 30 days of admission to hospital Admission to intensive care unit within 30 days of admission to hospital The full statistical analysis plan for this trial includes the flexibility to allow for pandemics of different severity. 				
	Dexame	hasone, given as adjuvant therapy in addition to standard care.			
Investigational	Form:	Liquid			
Medicinal Product	Dose:	6 mg once daily for 5 days from randomisation			
	Route:	Oral (or enteral through nasogastric tube)			

3 ABBREVIATIONS

AE	Adverse event
ASAP	Adjuvant Steroids in Adults with Pandemic Influenza
CI	Chief Investigator
COPD	Chronic Obstructive Pulmonary Disease
CFR	Case Fatality Ratio
CRF	Case Report Form
DMC	Data Monitoring Committee
GCP	Good Clinical Practice
GP	General Practitioner
ICH	International Conference of Harmonisation
ICU	Intensive Care Unit
IMP	Investigational Medicinal Product
ITT	Intention-to-treat
LOS	Length of stay in hospital
MHRA	Medicines and Healthcare products Regulatory Agency
NCTU	Nottingham Clinical Trials Unit
NETSCC	NIHR Evaluation, Trials and Studies Coordinating Centre
NHS	National Health Service
NIHR	National Institute for Health Research
PHE	Public Health England
R&D	NHS Trust R&D Department
REC	Research Ethics Committee
SAE	Serious Adverse Event
SAR	Serious Adverse Reaction
SOP	Standard Operating Procedure
SPC	Summary of Product Characteristics
SUSAR	Suspected Unexpected Serious Adverse Reactions
TMG	Trial Management Group
TSC	Trial Steering Committee
WHO	World Health Organisation

4 BACKGROUND AND RATIONALE

Pandemic influenza occurs when a new influenza A virus strain emerges which is antigenically distinct from circulating influenza strains, and which is able to infect humans, spreading efficiently from person to person causing significant clinical illness in a high proportion of those infected. Since the beginning of the 20^{th} century, there have been 4 influenza pandemics of varying severity. The devastating 1918 pandemic ('Spanish flu') caused by influenza A/H1N1 resulted in 20 to 50 million deaths worldwide, representing a case-fatality ratio (CFR) of 2 – 3%. Subsequent pandemics in 1957 (H2N2) and 1968 (H3N2) resulted in approximately 1 to 4 million deaths worldwide; CFR 0.1 to 0.4%. In contrast, the 2009 pandemic (H1N1) was much less severe. It affected mainly people aged below 55 years of age, and had a low case-fatality ratio (0.025%) in the UK similar to that of recent seasonal influenza viruses [1]. The timing and severity of future influenza pandemics remains unpredictable. There are currently no markers that will predict the pathogenicity or spread of a potential pandemic strain in the human population. Therefore, any plans for a future pandemic need to be flexible and take account of different possible scenarios from mild to severe.

Presentation and prognosis

Influenza virus infection is associated with a wide spectrum of illness, from no symptoms to pneumonia and death. During a pandemic, most people are expected to experience a minor influenza-like illness characterized by fever and cough typically lasting 7 to 10 days. Nevertheless, the UK Pandemic Influenza Preparedness Strategy 2011 recommends that for pandemic planning an estimated 1-4% of symptomatic patients should be expected to require hospital care.[2] Patients may be admitted to hospital either because of influenza-related exacerbations of underlying co-existing illnesses such as chronic obstructive pulmonary disease (COPD), or due to complications of influenza infection such as pneumonia.

Following hospital admission, some patients deteriorate rapidly (within 24 hours) and require intensive care unit (ICU) level support for respiratory failure. The proportion who might require ICU support in a pandemic is difficult to predict, and a range of 15% to 25% of hospitalized patients has been suggested. In a severe pandemic, resource limitations will probably define the upper limit. In the 2009 H1N1 pandemic (a low severity pandemic), 17% of hospitalized patients were admitted to Level 2 or Level 3 care;[3] the median time from symptom onset to ICU admission was 6 days, and from hospital admission to ICU admission was 2 days.

A figure of up to 200,000 additional deaths across the UK over a 15 week period has been proposed for planning purposes in the UK Pandemic Influenza Preparedness Strategy 2011. In the 'low severity' 2009 pandemic, 7% of hospitalized patients with confirmed H1N1 influenza infection died [3].

Current standard therapy for influenza infection

In the management of patients admitted to hospital with influenza infection during a pandemic, current Clinical Management Guidelines recommend that all adults receive appropriate supportive care, including fluid replacement and oxygen supplementation, and antiviral therapy [4]. In addition, antibiotic therapy is recommended for all hospitalised adults except previously well adults with only influenza-related acute bronchitis.

Corticosteroids in influenza

During the early phase of illness, influenza A virus infection induces inflammatory (e.g. IL-6, IL-8) and T-helper type 1 (Th1) cell immune responses (e.g. IFN-induced protein 10 (IP-10), monokine induced by IFN-gamma (MIG), correlating with clinical illness [5]. Hypercytokinaemia is also recognized in patients with H5N1 influenza infection (e.g. IL-6,IL-10, MIG) with the highest levels found in patients who subsequently die [6]. Similar changes have been observed in patients with 2009 pandemic H1N1 infection [7]. Such inflammatory cytokines may suppress the hypothalamic-pituitary-adrenal axis resulting in relative adrenal insufficiency or compete with intracellular glucocorticoid receptor function, resulting in peripheral tissue steroid resistance [8]. Corticosteroids in low doses (e.g. hydrocortisone \leq 300mg per day or dexamethasone \leq 11.25 mg/day) downregulates proinflammatory cytokine transcription and has been shown to improve innate immunity in patients with septic shock [9, 10].

There are no completed randomised trials of the use of corticosteroids in patients with pandemic, avian or seasonal influenza infection. Corticosteroid use in influenza is widespread, non-systematic and marked by controversy [11-14]. During the 2009 pandemic, corticosteroid use in critically ill patients with H1N1 influenza was identified in 83 (30%) of 208 patients in a French registry [15], 107 (44%) of 245 patients in a South Korean cohort study and 126 (57%) of 220 patients in the European Society of Intensive Care Medicine H1N1 registry [16]. The heterogeneity of these cohort studies and non-randomised study designs preclude any firm conclusions regarding the risks or benefits of corticosteroids in influenza. In these cohort studies of critically ill patients with 2009 H1N1 pandemic influenza, the association of corticosteroids with mortality varied from a decrease in mortality, to no effect on mortality or an increase in mortality [13, 15-17]. Some cohort studies observed an association of corticosteroids with an increase in hospital acquired pneumonia, including fungal pneumonia [13, 15-17]. One cohort study of 83 hospitalised patients, of whom 17 received parenteral corticosteroids during the first 72 hours of illness, observed an increased risk of critical illness in corticosteroid treated patients (RR 1.8, 95% CI 1.2 to 2.8) [18]. Although multivariate analyses were employed in most of these studies, bias arising from confounding by indication (corticosteroids prescribed in the sickest patients as a 'treatment of last resort') cannot be fully discounted. The World Health Organisation (WHO) Clinical management of human infection with pandemic (H1N1) 2009 : revised guidance[19] recommended that systemic corticosteroids should not be given in severe influenza unless indicated for other reasons or as part of an approved research protocol. A Cochrane meta-analysis of studies of corticosteroids in influenza is on-going and will inform the yearly review of the Trial Protocol during the hibernation phase.

A) Effectiveness of corticosteroids in pneumonia. Trials of corticosteroids in patients hospitalised with community acquired pneumonia have reported varying results. Meijvis *et al* (n=304) observed a significant reduction in median length of stay together with greater declines in C-reactive protein (CRP) and interleukin-6 levels in the treatment arm (dexamethasone 5 mg for 4 days) [20]. In contrast, Snijders *et al* (n=213) did not detect a significant difference in clinical cure rate at Day 7 despite a faster rate of defervescence and decline in CRP levels in the treatment arm (prednisolone 40 mg for 7 days) [21]. An earlier small, inadequately powered, open-labelled trial by Mikami *et al* (n=31), did not detect any statistical difference in length of stay between groups [22].

In patients with severe community acquired pneumonia admitted to intensive care (ICU) [23], Confalonieri *et al* found hydrocortisone was significantly associated with improved oxygenation and a reduction in multiple organ dysfunction score on Day 8, and a reduction in delayed septic shock. This trial was stopped early (n=46) per protocol after the upper stopping boundary for improvement in oxygenation (PaO₂/FiO₂ ratio) was achieved. A significant reduction in length of stay (13 v 21 days, p = 0.03) and mortality (0% v 30%, p=0.009) was also observed.

B) Effectiveness of corticosteroids in sepsis. A systematic review of trials examining the benefit of corticosteroids in severe sepsis and septic shock in adults identified [24] 12 randomized or quasi randomised trials (n=1228) comparing low dose corticosteroids (hydrocortisone \leq 300mg per day (equivalent to dexamethasone 11.25 \leq mg/day)) for \geq 5 days with placebo or supportive care. The 28-day mortality for treated versus control patients was 37.5% versus 44.1% (RR 0.84, 95% CI 0.72 to 0.97). These results included the study by Confalonieri *et al*, 2005. Similar results were observed when this trial was removed from the analysis (RR 0.87, 95% CI 0.77 to 0.98). These studies of corticosteroids in sepsis differ from the studies in community acquired pneumonia in the timing of corticosteroid intervention; occurring later in the disease process when severe sepsis or septic shock was evident.

Potential harm of corticosteroids

A systematic review of corticosteroid trials in severe sepsis and septic shock did not identify any increased risk of gastroduodenal bleeding, superinfection or neuromuscular weakness. An association with an increased risk of hyperglycaemia (RR 1.16, 95% CI 1.07 to 1.25) and hypernatraemia (RR 1.61, 95% CI 1.26 to 2.06) was noted.

Of trials in community acquired pneumonia, Meijvis et al observed that hyperglycaemia was commoner in the treatment group, while Snijders *et al* noted that the risk of hyperglycaemia requiring additional therapy was non-significantly higher in the treatment group (2.3% of 104 v 0.9% of 109, p=0.27) [20, 21]. Snijders et al observed an increase in late failures in corticosteroid treated patients compared to controls; described as the need for an additional course of antibiotics, need for another or prolonged course of prednisolone or development of a parapneumonic effusion necessitating additional therapy. Rebound inflammation due to the withdrawal of corticosteroids may explain this finding. In contrast, Meijvis *et al*, did

not observe any differences in late failure. This may relate to relative differences between the half-lives of the different corticosteroids tested (prednisolone vs dexamethasone).

A meta-analysis of trials investigating the use of corticosteroids in acute bacterial meningitis observed that participants treated with corticosteroids had an increase in recurrent fever (RR 1.27, 95% CI 1.09 to 1.47) [25]. The rate of persistent fever was lower in the corticosteroids treated patients (RR 0.29, 95% CI 0.12 to 0.70) while other complications (including gastrointestinal haemorrhage) occurred in similar proportions of treatment and control groups.

Choice of trial intervention

Dexamethasone, compared to prednisolone, has a) minimal mineralocorticoid activity and does not affect sodium and water balance, thus avoiding potential problems with fluid retention which are not uncommon in severe viral pneumonitis, and b) a comparatively long biological half-life of 36 to 54 hours; thus extending the pharmacological effects of a 5 day treatment course to over 11 days and potentially offering protection against late failures due to rebound inflammation.

Description of study intervention

The study intervention is dexamethasone administered as an oral liquid preparation, within 24 hours of hospital admission. The regimen is 6 mg once daily for five days. Dexamethasone 6 mg is equivalent to prednisolone 40 mg or hydrocortisone 160 mg.

The oral liquid preparation will enable the vast majority of eligible participants to receive the intervention except those who are either strictly 'nil by mouth' or are unable to swallow. For some of these participants, administration via an enteral feeding tube will be possible. This approach is similar to the manner in which oseltamivir (no IV formulation licensed at the time) was administrated during the 2009 pandemic, when only a small proportion (less than 3%([26], [27])) of patients in intensive care received 'off-licence' intravenous antiviral therapy.

5 OBJECTIVES

5.1 Primary Objective

To determine whether during a pandemic, for adults (≥16 years) hospitalised with an influenza-like illness, a 5-day course of dexamethasone started within 24 hours of admission to hospital, in addition to standard care, is associated with a lower risk of death or admission to intensive care compared to placebo.

5.2 Secondary Objectives

To determine whether dexamethasone given in addition to standard care is associated with a reduction in the length of hospital stay, the frequency of hospital readmission and/or the frequency of GP consultations after discharge compared to placebo. If dexamethasone is effective, the study will also evaluate its cost-effectiveness.

6 TRIAL DESIGN

[figure not shown]
6.1 Summary of Trial Design

The ASAP trial is a **pragmatic multi-centre double-blind randomised placebo-controlled trial**. The trial design is based on the event of a high-severity pandemic; this being the default position at the start of a pandemic when the severity of a pandemic may not yet be apparent.

The trial will be set-up pre-pandemic. Once set-up is complete and the required approvals have been obtained, the trial will be placed into 'hibernation'. It will be activated during an influenza pandemic only if instructed by the National Institute for Health Research (NIHR). During the hibernation phase, regular review (at least annually) of trial procedures and sites will ensure that the trial is maintained in a state in which it can be rapidly activated to start recruitment in the event of a pandemic. If the NIHR activate the trial it will move to a pre-activation phase of 4-6 weeks. This final phase of trial set-up will include production and distribution of the trial drug and trial materials, finalisation of trial procedures, and a check of site readiness prior to beginning recruitment. A summary of the trial phases is shown in Figure 1.

Figure 1: Phases of ASAP trial

Based on a high-severity pandemic the trial will recruit 2200 patients, and flexibility has been included in the design of this trial to allow for pandemics of lower severity. Detailed information can be found in the Statistical Analysis Plan. The final sample size will be determined in conjunction with the Trial Steering Committee during the activation phase of the trial, once information about the severity of the pandemic is available. It is anticipated that there will be up to 50 centres participating in the UK, covering a wide geographical spread.

Adults (≥16 years) admitted to hospital with an influenza-like illness will be screened for entry into the trial within 24 hours of admission to hospital. Once consent for trial participation has been obtained, eligible patients will be randomised into the trial. Participants will be allocated to receive either dexamethasone or placebo. Both will be given as a liquid (orally or via a nasogastric feeding tube) once a day for 5 days whilst the participant is in hospital, or continued at home if the participant is discharged within 5 days of admission to hospital. All other clinical care will be according to national clinical management guidelines for pandemic influenza.

Routinely available data recorded in hospital records at the time of hospital admission will be collected once consent for trial participation has been obtained. Data on outcome will be collected from hospital

records upon discharge from hospital, or on Day 30 whichever is sooner (Day 1 = day of admission to hospital).

Participants will be sent a postal follow-up questionnaire to complete 30 days after hospital discharge. This will ask whether they have consulted their GP or been readmitted to hospital since being discharged from hospital. In addition, for those who were discharged within 5 days of admission and given their trial treatment to take home, information about treatment compliance will be requested. Participants who do not return this follow-up questionnaire within seven days of the expected completion date will be contacted by telephone by a member of the Nottingham Clinical Trials Unit (NCTU) to request the information. If a participant remains hospitalised at Day 60, completion of the follow-up questionnaire is not required. Patient outcome data for these patients will be collected from hospital-based system records.

[figure not shown]
Participants do not have any additional study visits.

Participants are considered to be in the trial once the trial treatment pack label has been completed (randomisation) until the follow-up questionnaire has been received by the NCTU (or, when a participant, who fails to return the questionnaire, provides the answers over the telephone instead). For any participants that die, inclusion in the trial will be from randomisation until the date of the participant's death. The participant will be considered lost to follow-up if the questionnaire is not returned and the NCTU are unable to contact the participant by telephone.

Please see Figure 2 for an overview of the trial design.

Figure 2: Overview of trial design

*Data collected at discharge or Day 30 if the patient remains hospitalised, whichever is sooner. In event of death data will also be collected. ** For patients hospitalised ≥60 days, no follow-up questionnaire is required; patient outcome data will be collected from hospital-based systems

6.2 Outcome measures

6.2.1 Primary outcome

Admission to intensive care unit or death, within 30 days of admission to hospital.

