6.3.2 Inclusion Criteria

During an influenza pandemic, patients are eligible for entry into the trial if they:

- are ≥ 16 years of age
- have been admitted to hospital within the previous 24 hours with a clinical diagnosis of an influenzalike illness
- have given consent (see section 6.4.2)

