6.3.3 Exclusion Criteria

Patients are not eligible for the trial if ANY of the following apply at the time of admission to hospital:

- known to be taking oral or IV corticosteroid treatment
- require treatment with oral or intravenous corticosteroids upon admission to hospital as standard treatment for comorbid illness
- known to be on insulin or oral medication for the treatment of diabetes mellitus
- known contra-indication to dexamethasone or any of the excipients (please refer to current version of SPC)

Where a patient is entered into the trial and later found to meet any of the exclusion criteria detailed above, continuation of trial treatment will be discontinued. Data will continue to be collected unless the participant specifically withdraws their consent to this. Please see section 7.5 for further information.

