6.4.2 Consent

The challenges of obtaining consent for a trial of an acute intervention in an emergency setting within the context of a pandemic are recognised.

Severe pandemic influenza constitutes a medical emergency; these patients can deteriorate rapidly and dramatically – the average time from hospital admission to ICU admission was 1 day in the 2009 pandemic. In addition, the context of a pandemic means that acute health care resources will be exceptionally stretched, through a combination of high healthcare demand and high levels of staff sickness. These challenges to the clinical service will also impact significantly on research delivery. Recruitment to the ASAP trial must not result in any significant delay to patient care, either to the potential participant or to other patients not being approached about the trial. Therefore consent for trial participation needs to be integrated into routine clinical care during a pandemic. This means approaching patients and their families whilst they are being assessed and triaged at hospital admission, and offering participation in a way that minimises disruption to patient care. Thus written consent for the trial will be obtained from potential participants using a short, single page combined information sheet and consent form at hospital admission points (see Figure 3). A full information leaflet will also be given to participants to read at a later time.

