8 SAFETY REPORTING

The definition of a serious adverse event (SAE) is problematic in the context of the ASAP trial since participants are likely to be critically ill patients and progression of pandemic influenza can lead to significantly life threatening and serious conditions, which are outcomes for this trial.

Events that are part of the natural history of the primary disease process or expected complications of critical illness will not be reportable as serious adverse events.

The principal investigator at a site will need to distinguish between an SAE that is possibly, probably or definitely related to treatment (i.e. a suspected adverse reaction (SAR) – see definition below) and an SAE that arises from disease progression or has another cause.

The study intervention (dexamethasone) is a commonly used drug for which the safety profile is well established. For this reason, only serious unexpected suspected adverse reactions (SUSARs) should be reported on an SAE form for this trial.

The trial will also capture other serious adverse events (SAEs), which are pre-specified outcomes in the trial. These will not be reportable on an SAE form but will be captured on the CRF and include the following:

- Death due to progression of the underlying disease or co-morbid illness
- Admission to the intensive care unit due to progression of the underlying disease or co-morbid illness
- Prolongation of hospital stay due to progression of the underlying disease or co-morbid illness

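### The primary outcome counts ICU admissions from hospital admission rather than from randomisation, so any ICU admission before randomisation is an event in either arm that treatment cannot affect

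*Protocol*

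**What the plan says.** Protocol 6.2.1 sets the primary outcome as "Admission to intensive care unit or death, within 30 days of admission to hospital". The synopsis and section 9.1 (high severity pandemic) use the same window, and secondary outcome 6 in 6.2.2 applies it to ICU admission alone. Section 6.1 anchors follow-up with "Day 1 = day of admission to hospital".

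Entry comes later than that. Section 6.3.2 admits patients who "have been admitted to hospital within the previous 24 hours with a clinical diagnosis of an influenzalike illness", and under 6.1 and 6.4.3 a patient is in the trial only when the pack label is completed. The exclusions in 6.3.3 concern current steroid use, a need for steroids on admission, treated diabetes, and contra-indication to the product. None concerns intensive care. Section 6.4.5 has critical care admission recorded on the CRF without limiting it to admissions after randomisation.

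On timing, section 4 says that some patients need ICU-level support within 24 hours of hospital admission, and gives a median of 2 days from hospital to ICU in the 2009 pandemic. Section 6.4.2 says "the average time from hospital admission to ICU admission was 1 day in the 2009 pandemic".

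**The concern.** The primary objective asks whether treatment started within 24 hours of admission lowers the risk of ICU admission or death. An ICU admission that happened before the pack was opened cannot be prevented by what is in it. Under the current definition it still counts, with the same expected frequency in each arm.

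These fixed events add equally to both arms' rates, so the relative risk moves toward 1 and the trial estimates something smaller than the effect of treatment on events that could still be prevented. The sample size in 9.2 makes no allowance for this: its 25% ICU rate is for all those admitted to hospital, and its only inflation is 5% for non-compliance and loss. Recruitment is planned to finish within one wave of about six weeks with no meaningful interim efficacy analysis expected (9.3), so there would be little chance to correct the definition once the trial is active.

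**Working it through.** **Inputs from section 9.2.** Control rates: 35% die, 25% go to ICU, and 50% of ICU patients die. The composite is 0.35 + 0.25 − 0.125 = 0.475. Relative reduction 15%, power 90%, inflation 5%. Alpha is not stated for the binary outcome; two-sided 5% and 1:1 allocation are assumed because they reproduce Table 2. The 1% alpha given for low/moderate severity does not (it gives 3,036 without, or 3,096 with, continuity correction).

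**Reproducing the stated figure.** p1 = 0.475, p2 = 0.85 × 0.475 = 0.40375, d = 0.07125, p̄ = (p1 + p2)/2.

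- n0 = [1.96·√(2p̄(1−p̄)) + 1.2816·√(p1(1−p1) + p2(1−p2))]² / d² = 1,017.6
- With continuity correction: n = (n0/4)·[1 + √(1 + 4/(n0·d))]² = 1,045.5, so 1,046 per arm
- Inflated: 1,046/0.95, rounded up to 1,102 per arm, total **2,204**, as in Table 2

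At 2,200 randomised, 2,200 × 0.95/2 = 1,045 per arm are analysed. Inverting the correction, n0 = (n − 1/d)²/n, and power = Φ{[√n0·d − 1.96·√(2p̄(1−p̄))]/√(p1(1−p1) + p2(1−p2))} = 90.0%.

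**Definition as written.** Let q be the share of all participants already admitted to ICU at randomisation. The protocol does not give q, so a range is assumed. It is also assumed that the 15% reduction applies only to later events. The control rate stays at 0.475 and the treated rate becomes q + 0.85 × (0.475 − q). For q = 5% this is 0.05 + 0.85 × 0.425 = 0.41125, and 1 − 0.41125/0.475 = 13.4%.

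**Definition restricted to events after randomisation.** Those already in ICU contribute death only. Applying the protocol's 50% ICU mortality to them, the control rate is 0.475 − q/2 and the treated rate is 0.85 times that.

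| q | q as share of the 25% ICU rate | Apparent reduction as written | Power as written, N = 2,200 | N for 90% as written | Control rate after change | Power after change, N = 2,200 |
|---|---|---|---|---|---|---|
| 0% | 0% | 15.0% | 90.0% | 2,204 | 47.5% | 90.0% |
| 1% | 4% | 14.7% | 88.7% | 2,298 | 47.0% | 89.4% |
| 2.5% | 10% | 14.2% | 86.6% | 2,454 | 46.25% | 88.6% |
| 5% | 20% | 13.4% | 82.4% | 2,750 | 45.0% | 87.0% |
| 10% | 40% | 11.8% | 72.0% | 3,528 | 42.5% | 83.7% |

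The change restores 15% as the effect being estimated. It recovers part of the lost power, not all of it.

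**The case against.** **The size rests on q, which nobody has stated.** This stands. Patients are approached during assessment and triage at admission points (6.4.2), packs are kept where influenza patients are admitted (6.4.3), and the first dose follows consent as soon as possible (7.1.1). Twenty-four hours is an outer limit. The 10% row would mean that 40% of all ICU admissions precede randomisation. At q = 1% the loss is 1.3 points of power.

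**The evidence on timing is mixed.** This also stands. The 1-day average in 6.4.2 sits beside a 2-day median in section 4 for the same pandemic. A reader might infer from the safety section, which says "participants are likely to be critically ill patients", that many will be in ICU at entry. That sentence explains SAE reporting and does not describe status at randomisation. The same section treats ICU admission through progression as an outcome. Emergency enrolment (6.4.2.2, 6.4.2.3) shortens the time to randomisation at least as much as it admits sicker patients.

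**The 15% in 9.2 is stated for the composite as defined.** True, so 9.2 is not an arithmetical error. But for the whole composite to fall by 15%, later events must fall by 0.15 × 0.475/(0.475 − q): 15.8% at q = 2.5%, 16.8% at 5%, 19.0% at 10%. The dilution then appears as a more demanding assumption about the drug.

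**The SAP or the steering committee could deal with it.** They could add a rule or a sensitivity analysis, and section 9 leaves the final primary outcome to the committee. But the protocol itself fixes the start of the window, and followed as written it counts these events.

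**Conclusion.** The point holds as a definitional weakness that is cheap to correct. The outcome window opens before randomisation, patients already in ICU may enter, and the protocol itself expects some ICU need within 24 hours. ICU admissions before randomisation are therefore primary events in both arms.

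Only the ICU component is affected, since a death cannot precede randomisation. The loss is about 1 to 3 points of power if q is 1% to 2.5%, and about 8 to 18 points if q is 5% to 10%. These figures assume two-sided 5% alpha, 1:1 allocation, and a 15% reduction confined to later events.

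A reader might go further and infer that the trial could show a false benefit, or that its primary analysis is invalid. The protocol does not support this: events before allocation are expected equally in both arms, so the consequence is dilution and lost power. Nor does it support a claim that the loss must be large, because q is unknown and the recruitment process points to a low value.

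**What to change.** 1. In the synopsis, 6.2.1 and 9.1, define the primary outcome as *admission to ICU after randomisation, or death, within 30 days of randomisation*. Alternatively, keep the end date at 30 days from hospital admission and count only events after randomisation; this leaves the existing Day 30 data collection unchanged. Either way, state where the 30 days start. A participant already in ICU at randomisation then contributes death only.
2. Align secondary outcome 6 in 6.2.2.
3. Record date and time of ICU admission and of randomisation on the CRF. ICU length of stay is already a secondary outcome and section 16 costs ICU by the hour, so the extra burden is small.
4. Report by arm the number already in ICU at randomisation.
5. In 9.2, state that the 47.5% control rate includes all ICU admissions from hospital admission, and describe the power accordingly: at 2,200, about 89% for q of 1% to 2.5%, 87% at 5% and 84% at 10%, if half of those already in ICU die.
6. Reconcile the two hospital-to-ICU times in section 4 and 6.4.2.

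Eligibility need not change. The cost is wording, two date-and-time fields and a slightly lower control event rate. Death only for a few participants and the composite for the rest is a mixed endpoint, which the count in item 4 makes visible. The protocol is reviewed at least annually during hibernation (6.1), so the change can be made before activation.
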